#### **8.8.6 Potential Serious Hepatotoxicity**

For a subject who experiences an elevation in AST or ALT that is  $\geq 3$  times the ULN, a total bilirubin level should also be evaluated. If the total bilirubin is  $\geq 2$  times the ULN, complete an IRE form, etc, with all values listed and also report as an AE in the source documents and eCRF.

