### 3.4 Trial Visit Window

Data at each time point will be summarized using data at the time point recorded in the case report form (these data will not be summarized at the time of withdrawal or follow-up examination). Unscheduled visit data will not be used. For the criteria of potentially clinically significant laboratory test values, vital signs, body weight, and ECG and the categorical analysis of QT interval as corrected by Fridericia's formula (QTcF) interval to be summarized at any time other than the time points, withdrawal and unscheduled visit data will also be used.

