### **9.3 Clinical Laboratory Data**

For each quantitative laboratory parameter, descriptive statistics of actual measurements and changes from baseline at each time point will be calculated.

For each quantitative laboratory parameter, measured values will be classified as “lower than the lower limit of the reference range,” “within the reference range,” and “higher than the upper limit of the reference range” using the reference ranges specified by the central laboratory, and a shift table from baseline in each period will be produced.

For each qualitative laboratory parameter, a shift table from baseline in each period will be produced.

The number and proportion of subjects in whom any measurement after IMP administration in each period up to before IMP administration in the next period (if the IMP is to be administered in the next period) meets the criteria for potentially clinically significant laboratory test values (Appendix 1) will be determined. A listing of subjects who meet the criteria will be provided.

The number and proportion of subjects in whom alanine aminotransferase (ALT), aspartate aminotransferase (AST), and total bilirubin (TBL) after IMP administration in each period up to before IMP administration in the next period (if the IMP is to be administered in the next period) meet Hy’s Law criteria ( $ALT \text{ or } AST \geq 3 \times \text{upper limit of normal [ULN]}$  and  $TBL \geq 2 \times \text{ULN}$ ) will be determined. A listing of subjects who meet the criteria will be provided.

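### SAP 3.4 does not list Hy's Law among the analyses that may use unscheduled data, so a case met only on an unscheduled sample can be missing from CT-10.5.1

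*SAP*

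**What the plan says.** **SAP 3.4 (Trial Visit Window)** makes three statements in order.

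- It sets the rule for by-time-point summaries: "Data at each time point will be summarized using data at the time point recorded in the case report form". A parenthesis adds that "these data will not be summarized at the time of withdrawal or follow-up examination".
- A separate sentence, with no limit on its scope, says "Unscheduled visit data will not be used".
- An exception follows. It opens "For the criteria of potentially clinically significant laboratory test values, vital signs, body weight, and ECG and the categorical analysis of QT interval" (the QTcF categories), covers those analyses where they are not tied to a time point, and ends "withdrawal and unscheduled visit data will also be used". Hy's Law is not among the named analyses, and follow-up is not among the readmitted data.

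**SAP 9.3 (Clinical Laboratory Data)** defines two per-period counts. The PCS count takes "any measurement after IMP administration in each period up to before IMP administration in the next period". The Hy's Law count takes ALT, "aspartate aminotransferase (AST), and total bilirubin (TBL) after IMP administration in each period", with the same end of window. Its criterion is ALT or AST ≥3×ULN with total bilirubin ≥2×ULN. Neither definition excludes a type of visit. Hy's Law has its own table and listing, CT-10.5.1 and CT-10.5.2, separate from the PCS pair CT-10.4.1 and CT-10.4.2.

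**Protocol 8.8.6** says that when AST or ALT reaches 3×ULN, "a total bilirubin level should also be evaluated". If bilirubin is ≥2×ULN, the case goes on an IRE form and is also reported as an AE. Protocol 8.8.1 lists potential serious hepatotoxicity as an immediately reportable event and allows the investigator to repeat or add laboratory tests.

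**The concern.** The paired liver criterion can be completed on a repeat or additional sample, taken because transaminases were already raised. Such samples will often be unscheduled. The SAP readmits unscheduled samples for single-parameter PCS flags but not for the paired criterion, and its two governing sections give different instructions for that count. Two programmers working in good faith could produce different versions of CT-10.5.1 from the same data. One of those versions could show no case while the safety database holds an IRE for potential serious hepatotoxicity.

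**Working it through.** The plan states no figure on this point, so the check sets the passages side by side.

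**1. What each section does with each type of sample**

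| Sample | Hy's Law, SAP 3.4 | Hy's Law, SAP 9.3 | Laboratory PCS, SAP 3.4 | Laboratory PCS, SAP 9.3 |
|---|---|---|---|---|
| Scheduled, post-dose | in | in | in | in |
| Unscheduled | out (flat sentence, no exception) | in | in (exception) | in |
| Withdrawal | not clearly out, not readmitted | in | in (exception) | in |
| Follow-up | not clearly out, not readmitted | in, after the last dose | not clearly out, not readmitted | in, after the last dose |

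The one direct contradiction is unscheduled samples for Hy's Law. The three entries marked as not clearly out are unresolved: the parenthesis in 3.4 belongs to the by-time-point sentence, whereas these counts are per period.

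**2. Whether the 9.3 window settles it**

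The PCS and Hy's Law counts share one window, and the PCS definition goes further by taking any measurement in it. Even so, 3.4 readmits withdrawal and unscheduled data for PCS explicitly. If the 9.3 window were enough, that exception would do no work. The natural reading is that the 3.4 default reaches per-period counts unless an exception is named, and none is named for Hy's Law.

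A likely origin (inference only): protocol 9.4.2.2 contains the PCS count but not Hy's Law. Hy's Law enters in SAP 9.3, and the 3.4 list may not have been extended to match.

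**3. When a case is lost**

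ALT, AST and total bilirubin are all in the standard chemistry panel (protocol 10.2), so each scheduled draw already gives the pair. A case drops out of CT-10.5.1 only if all three of these hold:

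- the paired criterion is not met on any scheduled post-dose sample in the period;
- it is met on an unscheduled sample;
- 3.4 is applied over 9.3.

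Invented illustration: Day 14 shows ALT 3.5×ULN with normal bilirubin, and an unscheduled Day 18 sample shows ALT 6×ULN with bilirubin 2.4×ULN. Protocol 8.8.6 makes this an IRE. SAP 9.3 counts it; SAP 3.4, read literally, does not.

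**4. Where the same case would still appear**

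- AE-1, because 8.8.6 requires an AE record, and the TEAE tables if it is treatment-emergent.
- LAB-1, the by-subject chemistry listing.
- CT-10.4.1 and CT-10.4.2 for ALT, since 6×ULN exceeds the Appendix 1 cut-off of 3×ULN.
- The same PCS outputs for bilirubin only if the value is ≥2.0 mg/dL. At 2.4×ULN that requires ULN ≥ 2.0/2.4 = 0.83 mg/dL.

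The PCS outputs work per parameter and do not pair the transaminase with bilirubin.

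**5. Follow-up samples**

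Period 2 dosing can fall between Day 30 and Day 36 of the Period 1 day count, so the Period 2 Day -1 draw falls on Day 29 to Day 35. That is 28 to 34 days after the Period 1 dose, and 9.3 counts it for Period 1. The follow-up examination is 28 days (+7) after the last dose, so 28 to 35 days. The schedule table is broken in the text available but appears to include laboratory tests there. Samples at nearly the same elapsed time therefore count after the first dose, while after the second their status is unstated in 3.4.

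**6. Scale**

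Assuming 36 subjects under a meal condition (the planned number of completers), one case moves the incidence from 0/36 = 0% to 1/36 = 2.8%.

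**The case against.** The strongest reply is that 9.3 defines the Hy's Law count by a post-dose window with no visit type excluded, so a sensible programmer would include every sample in it. On this view 3.4 governs by-time-point tables and the matter is one of wording. That largely stands for withdrawal and follow-up samples. It does not stand for unscheduled samples, where 3.4 has a flat exclusion and an exception list that leaves Hy's Law out.

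Two further replies stand. Because the scheduled panel already pairs the values, a case met on a scheduled sample is counted whatever a later repeat shows. And the unequal follow-up after the two doses has little effect on the fed-versus-fasting comparison: sequence is randomised 1:1, so each meal condition comes second in about half the subjects.

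A reader might go further and infer that 3.4 removes all withdrawal, unscheduled and follow-up samples from the liver count, or that a reportable liver case would disappear from the report. The documents support neither. The parenthesis about withdrawal and follow-up qualifies by-time-point data, and the AE listing, the chemistry listing and the PCS outputs would still carry the case.

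**Conclusion.** The point holds in a limited form. For unscheduled samples, SAP 3.4 and 9.3 give opposite instructions for the Hy's Law count, and 3.4 applied literally can leave an immediately reportable liver case out of CT-10.5.1 and CT-10.5.2. For withdrawal samples (Hy's Law) and follow-up samples (Hy's Law and laboratory PCS), the SAP is unclear rather than wrong: 3.4 does not plainly exclude them, does not readmit them, and does not match the 9.3 window.

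The effect is confined to the summary incidence and its listing. It requires a case met solely on a sample outside the schedule, and the documents give no event rate from which to judge how likely that is. The 2.8% against 0% shows scale only, because 36 is the planned number of completers, whereas the safety set is everyone dosed. No primary pharmacokinetic result is affected. The correction is still worth making, because the table concerned reports potential serious liver injury and the remedy costs almost nothing.

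**What to change.** In SAP 3.4:

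- add the Hy's Law criterion to the analyses that use withdrawal and unscheduled data;
- state that follow-up examination data are also used for the Hy's Law and laboratory PCS counts, assigned to the last meal condition received.

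Sections 3.4 and 9.3 then agree. If the sponsor does intend to exclude any of these samples, 9.3 should say so and the table footnotes should repeat it.

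The cost is one sentence and a change to a data filter. The counts may become slightly less favourable. No new data collection is needed.

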## 4 Sample Size

Country	Percentage (%)
Argentina	95
Australia	95
Austria	95
Belgium	95
Brazil	95
Chile	60
Costa Rica	60
France	95
Germany	95
Greece	95
Hungary	95
Italy	95
Japan	95
Mexico	95
New Zealand	95
Norway	95
Portugal	95
Spain	95
Switzerland	95

## 5 Statistical Analysis Sets

## 5.1 Food Effect Analysis Set

The food effect analysis set includes all subjects for whom  $C_{max}$ ,  $AUC_{\infty}$  or  $AUC_t$  could be calculated throughout Period 1 and Period 2.

## 5.2 Safety Analysis Set

The safety analysis set includes all subjects who were administered at least one dose of IMP.

## 5.3 Handling of Missing Data

No imputation procedures will be applied for missing data.

## 6 Primary and Secondary Outcome Variables

For the primary pharmacokinetic endpoint and secondary pharmacokinetic endpoints, refer to Table 2-1.

## 7 Disposition and Demographic Analysis

### 7.1 Subject Disposition

The number of subjects from whom informed consent is obtained and that of screen failures will be provided. The number and proportion of randomized subjects, and of those who received trial treatment, those who completed treatment after the start of IMP administration, those who discontinued treatment after the start of IMP administration, those who discontinued treatment by reason for discontinuation, and those included in each analysis set will be provided overall and by group (using the number of randomized subjects as a denominator for the proportion of subjects).

The number of subjects who received trial treatment during each period will be provided overall and by group. The number and proportion of subjects who discontinued treatment after IMP administration in each period up to before IMP administration in the next period (if the IMP is to be administered in the next period) and of those who discontinued treatment by reason for discontinuation will be determined overall and by group (using the number of subjects who received trial treatment in each period as a denominator for the proportion of subjects). The number of subjects who received trial treatment under each meal condition will be provided. The number and proportion of subjects who discontinued treatment and of those who discontinued treatment by reason for discontinuation will be determined by meal condition (using the number of subjects who received trial treatment under each meal condition as a denominator for the proportion of subjects).

### 7.2 Demographic and Baseline Characteristics

In each analysis set, descriptive statistics (the number of subjects, mean, standard deviation, minimum, median, and maximum; hereinafter the same applies) of age (years), body weight (kg), height (cm), and BMI ( $\text{kg}/\text{m}^2$ ), and frequency distribution (the number and proportion of subjects) of sex at birth, race, ethnicity, country where the trial is conducted, medical history (yes or no), complications (yes or no), and cytochrome P450 2D6 (CYP2D6) phenotypes (using classification for analysis indicated in Table-2; hereinafter the same applies) will be determined overall and by group. For body weight and BMI, screening values will be used.

### 7.3 Treatment Compliance

A listing of compliance with trial treatment will be provided.

#### **7.4 Prior and Concomitant Medication**

In the safety analysis set, the number and proportion of subjects who used medications from the day of IMP administration up to Day 14 in each period by drug class and preferred term of the World Health Organization Drug Dictionary (WHODD) Global B3 format version 01 Sep 2023 will be determined by meal condition (in subjects who received trial treatment under each meal condition).

#### **7.5 Protocol Deviations**

The number and proportion of randomized subjects with major deviations from the protocol for each deviation category (IMP administration, eligibility criteria, failure to discontinue the trial even when the subject meets the withdrawal criteria, procedures that affect evaluation of the primary endpoint, and use of prohibited concomitant medications) at each trial site will be determined overall and by group.

### **8 Efficacy Analyses**

Not applicable.

### **9 Safety Analyses**

The safety analysis set will be used for analysis by meal condition (in subjects who receive trial treatment under each meal condition). The baseline value will be the last measurement prior to IMP administration in each period.

#### **9.1 Extent of Exposure**

The number and proportion of subjects who received trial treatment will be determined.

#### **9.2 Adverse Events**

Adverse events will be coded using Medical Dictionary for Regulatory Activities (MedDRA) Ver. 27.1. The incidence of the following events will be summarized by system organ class (SOC) and preferred term (PT). If an AE occurs more than once in the same subject in the same period, the most severe event will be used in summarization.

- Treatment-emergent AEs (TEAEs)
- TEAEs by severity
- TEAEs with an outcome of death
- Serious TEAEs

A TEAE in each period is defined as a TEAE that occurs after IMP administration in each period up to before IMP administration in the next period (if the IMP is to be administered in the next period).

Similarly, IMP-related TEAEs will also be summarized.

### **9.3 Clinical Laboratory Data**

For each quantitative laboratory parameter, descriptive statistics of actual measurements and changes from baseline at each time point will be calculated.

For each quantitative laboratory parameter, measured values will be classified as “lower than the lower limit of the reference range,” “within the reference range,” and “higher than the upper limit of the reference range” using the reference ranges specified by the central laboratory, and a shift table from baseline in each period will be produced.

For each qualitative laboratory parameter, a shift table from baseline in each period will be produced.

The number and proportion of subjects in whom any measurement after IMP administration in each period up to before IMP administration in the next period (if the IMP is to be administered in the next period) meets the criteria for potentially clinically significant laboratory test values (Appendix 1) will be determined. A listing of subjects who meet the criteria will be provided.

The number and proportion of subjects in whom alanine aminotransferase (ALT), aspartate aminotransferase (AST), and total bilirubin (TBL) after IMP administration in each period up to before IMP administration in the next period (if the IMP is to be administered in the next period) meet Hy’s Law criteria ( $ALT \text{ or } AST \geq 3 \times \text{upper limit of normal [ULN]}$  and  $TBL \geq 2 \times \text{ULN}$ ) will be determined. A listing of subjects who meet the criteria will be provided.

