dSamples collected will be delivered to the central laboratory no later than 16 working days (excluding Saturdays, Sundays, and public holidays) before the scheduled date of administration of the IMP. Given that approximately 16 working days are required to obtain evaluation results, the schedule of IMP administration, etc, will be adjusted.

e

  
f A blood sample should preferably be collected at the Period 1 baseline examination, but may be collected at any time during the trial. If repeat blood sampling is necessary, a blood sample will be collected at any feasible time during the trial.

g Clinical laboratory tests comprise hematology, blood chemistry, and urinalysis. Blood sampling should be performed after at least 8 hours of fasting, to the extent possible.

h It is not necessary to perform this examination if fasting blood sampling was performed at screening (after at least 8 hours of fasting) and IMP administration is started within 14 days after screening examination.

i Performed before any other examinations. If the test result is positive, then whether the trial can be continued without any problems will be determined, and only after a repeat alcohol breath test is negative will the other examinations be performed.

j If a urine test is positive, then a serum test will be performed.

k If performed on the same day as blood collection, performing vital sign measurement and 12-lead ECG immediately after blood collection should be avoided and they should be performed prior to blood collection if at all possible.

l It is not necessary to perform this examination if IMP administration is started within 14 days after screening examination.

m From Day -3 to Day 8 of Period 1 and Period 2, subjects will keep a record of the date and time of bowel movements (with multiple entries if there are multiple bowel movements) and the condition of the stool.

n Performed only when withdrawal occurs during the period from administration of the IMP to completion of the Day 14 examination in Period 1 and Period 2. If the subject refuses to undergo the examination at the time of withdrawal or if the investigator decides that the examination cannot be performed due to an emergency or for other reasons, only feasible observations and tests will be performed.

Table 1.3-2      Acceptable Windows	
Standard Examination Time Point	Acceptable Windows for All Observations, Tests, and Assessments

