**1) Timing**

Refer to [Table 1.3-1](#).

Blood sampling should be performed after at least 8 hours of fasting, to the extent possible.

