**3) Methods**

Clinical laboratory tests for the items listed in the table in [Section 10.2](#) will be performed at specified time points using test kits supplied by the central laboratory. The central laboratory will analyze the samples and report the analysis results as needed to the investigator for review. The investigator will then date and sign the clinical laboratory test report to make it an official document. Whether or not blood and urine samples are collected, the date and time of blood sampling and the date and time of urine sampling, and whether or not the subject has fasted for at least 8 hours will be recorded in the source documents and the eCRF. As the results of clinical laboratory tests are reported directly from the central laboratory to the sponsor as an electronic file, they do not need to be recorded in the source documents or the eCRF. For the procedures for the collection, handling, and shipment of samples, the separately prepared procedures should be followed.

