## Appendix 1 Criteria for Identifying Laboratory Values of Potential Clinical Relevance

Laboratory Tests	Criteria
Chemistry	
AST (SGOT)	$\geq 3 \times$ upper limit of normal (ULN)
ALT (SGPT)	$\geq 3 \times$ ULN
Alkaline phosphatase	$\geq 3 \times$ ULN
LDH	$\geq 3 \times$ ULN
BUN	$\geq 30$ mg/dL
Creatinine	$\geq 2.0$ mg/dL
Uric Acid	
Men	$\geq 10.5$ mg/dL
Women	$\geq 8.5$ mg/dL
Bilirubin (total)	$\geq 2.0$ mg/dL
CPK	$\geq 3 \times$ ULN
Prolactin	$>$ ULN
Hematology	
Hematocrit	
Men	$\leq 37\%$ and decrease of $\geq 3$ percentage points from Baseline
Women	$\leq 32\%$ and decrease of $\geq 3$ percentage points from Baseline
Hemoglobin	
Men	$\leq 11.5$ g/dL
Women	$\leq 9.5$ g/dL
White blood count	$\leq 2,800/\text{mm}^3$ or $\geq 16,000/\text{mm}^3$
Eosinophils	$\geq 10\%$
Neutrophils	$\leq 15\%$
Absolute neutrophil count	$\leq 1,000/\text{mm}^3$
Platelet count	$\leq 75,000/\text{mm}^3$ or $\geq 700,000/\text{mm}^3$
Additional Criteria	
Chloride	$\leq 90$ mEq/L or $\geq 118$ mEq/L
Potassium	$\leq 2.5$ mEq/L or $\geq 6.5$ mEq/L
Sodium	$\leq 126$ mEq/L or $\geq 156$ mEq/L
Calcium	$\leq 8.2$ mg/dL or $\geq 12$ mg/dL
Glucose	
Fasting	$\geq 100$ mg/dL
Non-Fasting	$\geq 200$ mg/dL
Total Cholesterol, Fasting	$\geq 240$ mg/dL
Triglycerides, Fasting	$\geq 150$ mg/dL

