## Appendix 4 List of Summary Tables

CT-1.1	Subject Disposition (All Subjects)
CT-1.2	Analysis Set (Randomized Subjects)
CT-2.1	Reasons for Discontinuation (Randomized Subjects)
CT-2.2	Reasons for Discontinuation by Period (IMP Administered Subjects)
CT-2.3	Reasons for Discontinuation by Food Condition (IMP Administered Subjects)
CT-3.1	Demographic and Baseline Characteristics (Food Effect Analysis Set)
CT-3.2	Demographic and Baseline Characteristics (Safety Analysis Set)
CT-4.1	Concomitant Medications Taken during IMP Administration Period (Safety Analysis Set)
CT-4.2	Summary of Major Protocol Deviations by Center and Type of Deviation (Randomized Subjects)
CT-7	Extent of Exposure (Safety Analysis Set)
CT-8.1	Overall Summary of Adverse Event (Safety Analysis Set)
CT-8.2.1	Incidence of TEAEs by System Organ Class and MedDRA Preferred Term (Safety Analysis Set)
CT-8.2.2	Incidence of Drug-related TEAEs by System Organ Class and MedDRA Preferred Term (Safety Analysis Set)
CT-8.3.1	Incidence of TEAEs by Severity by System Organ Class and MedDRA Preferred Term (Safety Analysis Set)
CT-8.3.2	Incidence of Drug-related TEAEs by Severity by System Organ Class and MedDRA Preferred Term (Safety Analysis Set)
CT-8.4.1	Incidence of TEAEs with an Outcome of Death by MedDRA System Organ Class and Preferred Term (Safety Analysis Set)
CT-8.4.2	Incidence of Drug-related TEAEs with an Outcome of Death by MedDRA System Organ Class and Preferred Term (Safety Analysis Set)
CT-8.5.1	Incidence of Serious TEAEs by System Organ Class and MedDRA Preferred Term (Safety Analysis Set)
CT-8.5.2	Incidence of Drug-related Serious TEAEs by System Organ Class and MedDRA Preferred Term (Safety Analysis Set)
CT-9.1	Listing of Deaths (Safety Analysis Set)
CT-9.2	Listing of Serious Adverse Events Other Than Death (Safety Analysis Set)
CT-10.1.1	Descriptive Statistics for Clinical Laboratory Test Results - Serum Chemistry (Safety Analysis Set)
CT-10.1.2	Descriptive Statistics for Clinical Laboratory Test Results - Hematology (Safety Analysis Set)
CT-10.1.3	Descriptive Statistics for Clinical Laboratory Test Results - Urinalysis (Safety Analysis Set)
CT-10.2.1	Shift Tables of Clinical Laboratory Test Results - Serum Chemistry (Safety Analysis Set)
CT-10.2.2	Shift Tables of Clinical Laboratory Test Results - Hematology (Safety Analysis Set)
CT-10.2.3	Shift Tables of Clinical Laboratory Test Results - Urinalysis (Safety Analysis Set)

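### SAP 9.3 summarises glucose, insulin, triglycerides and total cholesterol without using the recorded fasting status, so within-condition changes and shifts can be confounded with recent food intake

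*SAP*

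**What the plan says.** SAP 9.3 treats all quantitative laboratory parameters alike: "For each quantitative laboratory parameter, descriptive statistics of actual measurements and changes from baseline at each time point will be calculated". For the shift tables, values are classified "using the reference ranges specified by the central laboratory, and a shift table from baseline in each period will be produced". SAP 9 defines baseline without reference to fasting: "The baseline value will be the last measurement prior to IMP administration in each period". In SAP Appendix 4, serum chemistry has one descriptive table (CT-10.1.1) and one shift table (CT-10.2.1), and neither title mentions fasting.

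Protocol 8.7.1.1 says of the draws: "Blood sampling should be performed after at least 8 hours of fasting, to the extent possible". Under Methods it adds that "whether or not the subject has fasted for at least 8 hours will be recorded in the source documents and the eCRF". Protocol Table 10.2-1 includes glucose, insulin, triglyceride and total cholesterol in the chemistry panel.

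Elsewhere the documents do use fasting status:

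- SAP Appendix 1 sets glucose limits of 100 mg/dL or more fasting and 200 mg/dL or more non-fasting. Total cholesterol (240 mg/dL or more) has a fasting limit only, as does the row "Triglycerides, Fasting" (150 mg/dL or more). Insulin has no criterion.
- Exclusion criterion 10 has separate fasting and non-fasting glucose limits (126 and 200 mg/dL).
- A footnote to Protocol Table 1.3-1 says of the Period 1 baseline laboratory draw: "It is not necessary to perform this examination if fasting blood sampling was performed at screening (after at least 8 hours of fasting"), provided that dosing also starts within 14 days of screening.

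**The concern.** The plan collects the variable that says whether a glucose or lipid value is comparable with another, and uses it for the threshold criteria. It then drops it from the means, changes and shift tables for the same analytes. SAP 9.4 shows that a measurement condition can be fixed in one sentence: it restricts blood pressure and pulse rate to sitting values. SAP 9.3 has no counterpart for fasting.

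Three outputs are exposed:

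- **Mean change.** If a subject was fasted at baseline and not at a later draw, or the reverse, the change contains a food component.
- **Shift tables.** A value taken after a meal is judged against the same reference range as a fasting one, so eating alone can produce a shift to high.
- **Fasting-only criteria.** SAP 9.3 reports a number and proportion, and SAP 9 analyses subjects treated under each meal condition. A subject with no fasting post-dose triglyceride or cholesterol value cannot meet the criterion but would still appear in the denominator.

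Confirming safety is the secondary objective and clinical laboratory tests are a listed endpoint. Settling the rule before analysis avoids a post hoc choice if a metabolic change appears.

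**Working it through.** The plan states no figure here to reproduce. The check sets the texts side by side, then illustrates the size.

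**Text.** Non-fasting draws are permitted (Protocol 8.7.1.1) and identifiable (same section). No sentence in SAP 9 or 9.3 restricts or splits the descriptive or shift summaries by that status. The gap is confined to those summaries and the denominator, because Appendix 1 already conditions its glucose, triglyceride and total cholesterol limits on fasting.

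**Mean change.** Let q_base and q_post be the shares of non-fasting draws at baseline and post-dose, and d the non-fasting minus fasting difference. Then

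food component of the mean change = (q_post − q_base) × d.

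Neither q nor d is in the documents. All values below are assumptions, with d = 10 to 40 mg/dL for glucose and 20 to 100 mg/dL for triglycerides.

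| q_base | q_post | Glucose (mg/dL) | Triglycerides (mg/dL) |
|---|---|---|---|
| 0 | 0 | 0 | 0 |
| 0.20 | 0.20 | 0 | 0 |
| 0 | 0.10 | 0.10 × 10 to 0.10 × 40 = 1 to 4 | 0.10 × 20 to 0.10 × 100 = 2 to 10 |
| 0 | 0.30 | 0.30 × 10 to 0.30 × 40 = 3 to 12 | 0.30 × 20 to 0.30 × 100 = 6 to 30 |
| 0.30 | 0 | −3 to −12 | −6 to −30 |

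The last row shows only that the sign depends on which draws are less often fasted; the documents do not suggest that baseline draws are. No range is offered for insulin or total cholesterol.

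**Spread.** Equal shares remove the mean bias but not the added noise. If fasting status at the two draws is independent with the same share q,

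variance of change = SD² + 2q(1 − q)d².

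For glucose with an assumed fasting SD of change of 8 mg/dL, d = 20 and q = 0.10: 64 + 2 × 0.10 × 0.90 × 400 = 136, so the SD is √136 = 11.7 mg/dL.

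**Fed versus fasting.** The contrast between conditions carries the difference of the two food components. If q_post − q_base is the same under both conditions, that difference is zero.

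**Denominator.** With k subjects meeting a fasting-only criterion, N treated under a condition and m of them without a fasting post-dose value, the rule as written gives k/N. Among those who could be assessed, the proportion is k/(N − m), which is higher whenever k and m are above zero.

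**The case against.** The strongest reply is that the omission may have no practical effect. The protocol asks for an 8-hour fast before laboratory draws, and the Period 1 baseline draw can be skipped only on the strength of a fasting screening sample. With good compliance the food component is zero. Appendix 1 already applies fasting-specific limits, and individual chemistry values are listed (LAB-1). The tables are descriptive, in a trial of two single doses whose primary question is pharmacokinetic. All of this stands, and it limits the weight of the point.

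A reader might go further and infer three things that the documents do not support.

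- **That the by-meal-condition laboratory tables are uninterpretable.** Both periods permit outpatient visits at the later time points, and the order of conditions is randomized. Missed fasts should therefore fall largely alike on the fed and fasting conditions.
- **That the test meal itself enters these values.** As far as the schedule can be read, no laboratory draw falls at 3 or 9 hours post-dose. The table's columns are not fully legible, so this is a cautious reading.
- **That non-fasting draws cluster at Day 14.** Outpatient attendance is permitted, not required, and an outpatient can arrive fasted. Clustering is plausible but remains inference.

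What the reply does not answer is that the written rule mixes the two kinds of sample whenever a fast is missed, although the field that separates them is collected.

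**Conclusion.** The gap is real and modest. SAP 9.3 does not use recorded fasting status for the means, changes and shift tables of glucose, insulin, triglycerides and total cholesterol, although Appendix 1 uses it in the limits for three of these four. Within-condition changes and shifts can therefore be confounded with recent food intake.

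The size is unknown. It is zero if all draws are fasting. If the non-fasting shares are equal at baseline and post-dose, the mean bias is zero but the spread still increases. The illustrative shifts rest wholly on assumed shares and differences. Neither the fed-versus-fasting safety comparison nor the primary pharmacokinetic analysis is expected to be materially affected. This is an inexpensive improvement to descriptive safety tables, not a threat to the trial's conclusion.

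**What to change.** In SAP 9.3, for glucose, insulin, triglycerides and total cholesterol:

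1. Present descriptive statistics, changes from baseline and shift tables by recorded fasting status.
2. Base the change and shift summaries on pairs with at least 8 hours of fasting recorded at both baseline and post-dose. Show non-fasting values separately or list them.
3. For the fasting-only potentially clinically significant criteria, use as denominator the subjects with at least one fasting post-dose value under that meal condition.

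This needs a few sentences in the SAP and a filter on an existing eCRF field, with no new data. The cost is slightly longer tables and fewer subjects in the fasting-pair summaries. With 36 completers and all baselines fasting, a 10% non-fasting share at a post-dose draw would remove about 4 pairs per condition (0.10 × 36 = 3.6). A 30% share would remove about 11 (0.30 × 36 = 10.8). Because the excluded values are still shown or listed, none is lost from the report.
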